11.9.2	Secondary Endpoints	40
12	ETHICS/PROTECTION OF HUMAN SUBJECTS	40
12.1	Informed Consent Process	40
12.2	Subject Confidentiality	40
13	DATA MANAGEMENT AND MONITORING	41
13.1	Data Management Responsibilities.....	41
13.2	Data Capture Methods	41
13.3	Types of Data	41
13.4	Source Documents and Access to Source Data/Documents	41
13.5	Record Retention	41
14	References.....	43

LIST OF TABLES

Table 1: Cohorts and Dose Levels	12
Table 2. Example of dosing timeline	12
Table 3: Dosing and Administration.....	19
Table 4: Schedule of Assessments	22

LIST OF FIGURES

Figure 1: SAB-176 Vial Label.....	18
-----------------------------------	----

LIST OF ABBREVIATIONS

AE	Adverse Event
ALT	Alanine Aminotransferase
AST	Aspartate Aminotransferase
BMI	Body Mass Index
BUN	Blood Urea Nitrogen
CBC	Complete Blood Count
CFR	Code of Federal Regulations
CKD-EPI	Chronic Kidney Disease Epidemiology Collaboration
CLIA	Clinical Laboratory Improvement Amendment of 1988
CRF	Case Report Form
CRIS	Clinical Research Information System
ECG	Electrocardiogram
FDA	Food and Drug Administration
GCP	Good Clinical Practice
GFR	Glomerular Filtration Rate
HA	Hemagglutinin
HAC	Human Artificial Chromosome
HAI	Hemagglutination Inhibition
hIgG	Human Polyclonal IgG
IB	Investigator's Brochure
ICF	Informed Consent Form
ICH	International Conference on Harmonization
IgG	Immunoglobulin
IVIg	Immunoglobulin for Intravenous Use
IND	Investigational New Drug
IRB	Institutional Review Board
IV	Intravenous
K	Potassium
LDH	Lactate Dehydrogenase
MN	Microneutralization
Na	Sodium
NIH	National Institutes of Health
OTC	Over-the-Counter
PI	Principal Investigator
PK	Pharmacokinetics
PT	Prothrombin Time
PTT	Partial Thromboplastin Time
SAE	Serious Adverse Event/Serious Adverse Experience
SRCP	Safety Review and Communication Plan
SUSAR	Serious and Unexpected Suspected Adverse Reaction
TBD	To Be Determined
Tc	Transchromosomal
TKO	Triple Knockout
UDS	Urine Drug Screen
UP	Unanticipated Problem
UPnonAE	Unanticipated Problem that is not an Adverse Event

PROTOCOL SUMMARY

Full Title:	A Phase 1, Randomized Double-Blind, Placebo-Controlled, Single Ascending Dose Safety, Tolerability, and Pharmacokinetics Study of SAB-176 in Healthy Adults
Short Title:	SAB-176
Clinical Phase:	1
IND Sponsor:	SAB Biotherapeutics, Inc.
Conducted by:	PPD
Principal Investigator:	[name].
Sample Size:	27 subjects
Accrual Ceiling:	150 (up to 150 subjects screened to randomize a total of 27 subjects)
Study Population:	Healthy Volunteers aged 18 to 60 years
Accrual Period:	Start Date: TBD End Date: TBD
Study Duration:	Start Date: TBD End Date: TBD
Study Design:	Randomized, Double-Blind, Placebo-Controlled, Dose-escalating
Study Agent:	Active: SAB-176 Control: Normal (0.9%) saline
Primary Objective:	To evaluate the safety and tolerability of SAB-176 in healthy adults, following single intravenous administration at escalating dose-levels
Secondary Objectives:	
• To evaluate the pharmacokinetics of intravenously administered SAB-176 in healthy adults, following single intravenous administration at escalating dose-levels• To determine the ability of serum levels of SAB-176 to neutralize Type A and Type B influenza viruses• To evaluate the immunogenicity of SAB-176
Primary Endpoint:	Type and frequency of adverse events experienced by subjects receiving SAB-176 at escalating dose-levels, as compared to control saline
Secondary Endpoints:	
• Pharmacokinetic profile of intravenously administered SAB-176 in healthy adults• Serum Type A and B Hemagglutination Inhibition (HAI) Assays• Serum Type A and B Microneutralization (MN) Assays• Frequency and concentrations of antibodies caused by SAB-176, as measured by:
○ Anti-IgG antibodies using rheumatoid factor○ Anti-SAB-176

PRÉCIS

The administration of convalescent plasma or hyperimmune immunoglobulin G (IgG) is often used for treatment of infectious diseases. However, production of large quantities of anti-pathogen human plasma and/or immunoglobulin with high affinity and avidity antibodies currently requires donations by convalescent humans, a process that can limit availability for a number of reasons. One novel alternative source is transchromosomal (Tc) bovine that produce fully human polyclonal IgG (hIgG) de novo and mount a robust antibody immune response after vaccination.

This study will evaluate the safety, tolerability, and immunogenicity of SAB-176, a fully human polyclonal anti-Influenza IgG produced from transchromosomal bovine. Beginning with a low single-dose, subjects are randomized to receive either SAB-176 or a normal saline control, and evaluated on Study Days 1, 3, 7, 21, 42, and 90. The safety and tolerability is evaluated using symptoms, clinical laboratory tests, pharmacokinetics, and immunogenicity assays. Utilizing a series of stopping rules and a medical monitor, the dose will be escalated as safety and tolerability are established.

1 BACKGROUND INFORMATION AND SCIENTIFIC RATIONALE

1.1 Background

Influenza causes substantial morbidity and mortality worldwide despite available antivirals and vaccines. Influenza is responsible for 226,000 excess hospitalizations and 30,000 to 50,000 deaths each year in the United States alone (1). Effective therapeutics are needed to prevent mortality or morbidity in those afflicted with severe influenza. Human plasma (delivered as Fresh Frozen Plasma units) or human intravenous immunoglobulin (hIVIg) with anti-influenza antibodies have been proposed as treatments for severe influenza (2). A limitation with plasma or hIVIg is that large numbers of human plasma donors/units must be screened to identify those few with a higher-than-average hemagglutination inhibition (HAI) titers to multiple strains of influenza. However, recent clinical trials have not shown benefit to hospitalized patients with severe Type A influenza infections treated with human-derived anti-influenza plasma or hIVIg (3, 4).

SAB Biotherapeutics, Inc., has developed SAB-176 to address the production limitations and lack-of-clinical efficacy of human-derived plasma or hIVIg. SAB-176 is a unique anti-influenza hIgG containing fully human polyclonal IgG antibodies with extremely high HAI and microneutralization (MN) titers against past, current, and potentially future strains of Type A influenza (H1N1/H3N2) and both lineages of Type B influenza (Yamagata/Victoria). SAB-176 is purified from the plasma of immunized transchromosomal (Tc) bovines that were immunized with a quadrivalent recombinant hemagglutinin (HA) protein vaccine produced in insect cells. The HA antigens match the four influenza strains recommended yearly for the Northern hemisphere by the Center for Disease Control and Prevention (CDC).

Furthermore, Tc bovine hIgGs have an IgG1 subclass content of approximately 80-90% versus approximately 60% for human-derived IVIg. IgG1 strongly activates complement and effector cells (NK cells, neutrophils, monocytes, etc.) of the innate immune system. SAB-176 is therefore much different than human-derived anti-influenza hIVIgs. SAB Biotherapeutics believes that SAB-176's distinct attributes, in combination with early treatment of severe influenza disease, could demonstrate that the product reduces morbidity and mortality in patients with Type A and/or B influenza.

The genome of Tc bovines contains a human artificial chromosome (HAC) comprising the entire human Ig gene repertoire (human Ig heavy chain [IgH] and human kappa light chain) that reside on 2 different human chromosomes (hChr), specifically the IgH locus from hChr14 and the Immunoglobulin kappa (Igk) locus from hChr2. The system maintains the ability to use the genetic information provided by the immunoglobulin gene repertoires for generating the seemingly unlimited diversity of human polyclonal antibodies (pAbs).

Fully hIgG (hIgG/hIgk) can then be produced in these Tc bovines after vaccination with suitable antigens, and these animals produce up to 15 g/L of IgG antibodies in their plasma (similar to humans which have 7-16 g/L IgG). SAB-176 is an anti-influenza hIgG prepared in this system.

Tc bovines receive repeated doses of a quadrivalent recombinant HA protein vaccine produced in insect cells. Just prior to immunization of the Tc bovine, the HA proteins are mixed with adjuvants.

Plasma is collected using an automated plasmapheresis system. After collection of sufficient volume, plasma undergoes Quality Control testing, is frozen and stored. Once it is ready to be processed, qualified frozen plasma is thawed, pooled, fractionated by caprylic acid (CA) and clarified by depth filtration in the presence of filter aid. The clarified sample containing hIgG is further purified by affinity chromatography, first using an anti-human IgG kappa affinity column to capture hIgG pAbs and remove residual non-hIgG and bovine plasma proteins (BPP). The sample is subsequently passed through an anti-bovine IgG (bIgG) heavy chain specific affinity column to further remove residual IgG molecules that contain a bovine heavy chain. The hIgG fraction is then subjected to a Q Sepharose chromatography polishing step to further reduce impurities, nanofiltration, final buffer exchange, concentration and sterile filtration. Finally, the product is terminally filtered and filled into vials.

The drug product will be administered intravenously and will be diluted in saline per the clinical protocol.

1.2 Rationale

This study will evaluate the safety and pharmacokinetics of SAB-176. This will both advance treatments for Type A and Type B influenza viruses, as well as establish the safety of the platform that could be used to quickly develop therapeutics for other emerging infectious diseases.

2 STUDY OBJECTIVES

2.1 Primary Objective

- To evaluate the safety and tolerability of SAB-176 in healthy adults, following single intravenous administration at escalating dose-levels

2.2 Secondary Objectives

- To evaluate the pharmacokinetics of intravenously administered SAB-176 in healthy adults, following a single intravenous administration at escalating dose-levels
- To determine the ability of serum levels of SAB-176 to neutralize Type A and Type B influenza viruses
- To evaluate the immunogenicity of SAB-176, as measured by:
 - Anti-IgG antibodies using rheumatoid factor
 - Anti-SAB-176

3 INVESTIGATIONAL PLAN

3.1 General

Study size: 27 subjects (up to 150 subjects screened to randomize a total of 27 subjects)

Study duration: 1 year

Study duration of individual subjects (not including screening): 90 days

Sex distribution: males and females

Age range: 18 to 60 years

3.2 Study Design

This safety and tolerability study of intravenous (IV) SAB-176 consists of up to 4 single dose-levels or cohorts (cohort 1–4) in a double-blind, randomized, placebo-controlled dose-escalating cohort design. Four cohorts of 2–10 subjects each will be administered a single IV dose of SAB-176 or saline placebo. At very low doses, the concern is primarily allergic or T-cell activation/cytokine storm, so small cohort sizes should be utilized. As the target dose is approached, the sample size will increase to increase the likelihood of detecting toxicity events. The cohorts and dose levels are outlined in [Table 1](#).

Table 1: Cohorts and Dose Levels

Cohort	Number of Subjects Receiving SAB-176				Number of Subjects Receiving Saline Control
	1 mg/kg	10 mg/kg	25 mg/kg	50 mg/kg	
1	2				1
2		4			2
3			6		2
4				8	2

The number of subjects dosed will follow the limitations below:

- The first three subjects of each cohort will be dosed every other day (48-hour interval).
- For Cohorts 2–4, 48 hours after the third subject is dosed, up to 3 subjects may be dosed per day, until the cohort is completed, and no more than 8 subjects will be dosed per week.
- For cohorts 2, 3, and 4, additional dosing in the cohort may continue only after the safety committee recommends continuation after reviewing the safety data from the 3 initial subjects of the cohort.
- After the first three in each cohort, subsequent subjects will be observed for at least 4 hours before beginning the next infusion in the next subject.

Table 2. Example of dosing timeline

	Infusion Day								
	1	2	3	4	5	6	7	8	9
Subject 1	X								
Subject 2			X						
Subject 3					X				
Subject 4							X*		

Table 2. Example of dosing timeline (con't)

	Infusion Day								
	1	2	3	4	5	6	7	8	9
Subject 5							X (≥4 hrs post Subject 4)		
Subject 6							X (≥4 hrs post Subject 5)		
Subject 7								X	
Subject 8								X (≥4 hrs post Subject 7)	
Subject 9								X (≥4 hrs post Subject 8)	
Subject 10									X

* Additional enrollment in the cohort may continue only after the safety committee recommends continuation after reviewing the safety data from the three initial subjects of the cohort.

NOTE: Only 1 subject should be infused at any given time. An infused subject should be observed for at least four hours prior to beginning the next infusion.

Beginning with a low single-dose, subjects are randomized to receive either SAB-176 or placebo on Day 0. Subjects are then evaluated on Study Days 1, 3, 7, 21, 42, and 90.

3.3 Definitions for the Purpose of this Study

Definitions for the Purpose of this Study:

Enrolled

For the purpose of collecting data and samples and reporting adverse events (AEs), a subject will be considered enrolled beginning from when the informed consent form is signed until the subject is considered “screen failure”, “discontinued”, or “completed”.

Randomized

Subjects are considered randomized when they meet all of the following criteria:

- Enrolled (as defined above)
- Confirmation that the inclusion and exclusion criteria are met
- Randomization number is assigned

Screen Failures

Subjects are considered screen failures when they meet one or more of the following criteria after signing consent:

- Screening tests reveal that the subject is ineligible
- Subject withdraws consent before being randomized

Discontinued

Subjects are considered discontinued when they meet one or more of the following criteria:

- Subject withdraws consent after being randomized and prior to the completion of Day 90 (see Section 4.6)
- Subject is withdrawn after enrollment by Investigator (see Section 4.7) including lost to follow-up

Completed

Subjects are considered completed when they are followed through Study Day 90 and complete the final study follow-up visit (Study Day 90).

4 STUDY POPULATION

4.1 Research Subject Selection

Healthy volunteers will be recruited for this study.

4.2 Recruitment

Volunteers will be recruited through the posting of advertisements or via a pre-existing registry of potential subjects. All flyers and advertisements will be submitted to the Institutional Review Board (IRB) for approval.

4.3 Inclusion Criteria

1. Age \geq 18 years and \leq 60 years
2. Body mass index (BMI) of 19-32 kg/m²
3. Subjects must have values in normal ranges for basic labs (i.e., CBC, PT/INR, Chem-7, and LFTs), unless deemed not clinically significant by the PI.
4. Estimated glomerular filtration rate \geq 85 mL/min at screening, calculated using the Chronic Kidney Disease Epidemiology Collaboration (CKD-EPI) formula
5. Subjects must agree to:
 - Not take any prescription or over-the-counter (OTC) medications with the exception of acetaminophen, ibuprofen, vitamins, seasonal allergy medications, and/or contraceptive medications, or others unless approved by the study investigator, for a period 7 days prior to study drug administration (i.e., Day 0)

1) Use one of the following in order to avoid pregnancy:

- Females who are able to become pregnant (i.e., are not postmenopausal, have not undergone surgical sterilization, and are sexually active with men) must agree to use at least 2 effective forms of contraception from the date of the subject's signing of the informed consent form through 60 days after the last dose of study drug. At least one of the methods of contraception should be a barrier method.

- Males who have not undergone surgical sterilization and are sexually active with women must agree to use condoms plus have a partner use at least one additional effective form of contraception from the date of the subject's signing of the informed consent form through 60 days after the last dose of study drug.
- Neither females or males should donate oocysts or sperm for use in artificial insemination through 60 days after the last dose of study drug.

4.4 Exclusion Criteria

1. Any history of allergy, anaphylaxis, or severe reaction to beef products (including milk and gelatin)
2. Any history of allergy, anaphylaxis, or severe reaction to IVIg or human blood products
3. Any chronic medical problem/condition that require medications needed to maintain the subject's health. Exceptions to this restriction can be allowed for minor health conditions that are treated with Tylenol, over-the-counter non-steroidal anti-inflammatories, vitamins, seasonal allergy medications, or oral/transdermal/IUD contraceptives, etc. The study investigator will make a determination to exclude a subject based upon their medical history and the type and frequency of the drug substance.
4. History of cardiovascular disease, cardiomyopathy, heart failure, or unexplained syncope
5. Abnormal clinically significant 12-lead electrocardiogram (ECG), per PI discretion
6. Subjects who have been laboratory confirmed or clinically diagnosed with influenza within seven days prior to infusion (by subject history) will be deferred from infusion. Any subject with signs and symptoms of an active respiratory infection on the day of infusion will be deferred until the infection is cleared in the opinion of the investigator. Subjects that present with an active upper respiratory infection on the day of infusion will be tested with an FDA licensed Influenza A/B Antigen Test. Signs and symptoms constituting an upper respiratory infection include cough, sore throat, or rhinorrhea with or without fever.
7. Enrollment will be delayed for all patients who have other intercurrent infections (e.g., gastroenteritis, abscess, etc.).
8. Women who are breast-feeding
9. Positive urine or serum pregnancy test
10. Positive urine drug screen (UDS)
11. Clinically significant results, including laboratory results, as determined by study investigator
12. Positive rheumatoid factor
13. IgA deficiency (defined as IgA < 7 mg/dL)

14. Participation in another research study with receipt of any investigational drug within 5 half-lives or 30 days, whichever is longer, prior to study drug administration (i.e., Day 0) and until completion of the study
15. Participation in any other research study until the completion of the study
16. Receipt of blood products within 2 months prior to study drug administration (i.e. Day 0)
17. Receipt of any vaccination within 30 days prior to study drug administration (i.e. Day 0)
18. Any acute or chronic condition that, in the opinion of the Investigator, would limit the subject's ability to complete and/or participate in this clinical study

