6.3 Detailed Description of Assessments

6.3.1 Schedule of Assessments

The schedule of assessments is described in Table 3. The day when the subject is randomized is denoted as Study Day 0, the first day after enrollment is Study Day 1, etc.

Table 4: Schedule of Assessments

	Screen	Baseline							
Day +/- Window	-28 to -1	-1 to 0	1	2	3 (+1)	7 ± 1	21 ± 2	42 ± 3	90 ± 7
Evaluation/Procedure		Prior to infusion							
ELIGIBILITY									
Informed consent	X								
Demographics	X								
Medical history	X								
RANDOMIZATION/ STUDY DRUG									
Randomize subject		X							
Study drug administration		X							
STUDY PROCEDURES									
Assess Symptoms		X	X	X	X	X	X	X	X
Vital signs	X	X	X	X	X	X	X	X	X
Review of concomitant medications	X	X	X	X	X	X	X	X	X
Physical exam	X	if needed to assess AEs							
ECG	X								
Adverse events		X	X	X	X	X	X	X	X
SAFETY LABORATORY ^a									
CBC	X	X		X	X	X		X	X
PT/PTT	X	X		X	X	X		X	X
Reticulocyte Count	X	X		X	X	X		X	X
Chemistry Panel	X	X		X	X	X		X	
Urinalysis	X	X		X	X	X		X	
Quantitative Immunoglobulin	X	X		X	X	X	X	X	X
Rheumatoid factor	X	X		X	X	X	X	X	X
Urine biomarkers	X	X		X	X	X		X	
Pregnancy test (urine or serum)	X	X							
UDS	X	X							
REFERENCE PROCEDURE									
Stored serum for pharmacokinetics		X ^b	X	X	X	X	X	X	X
Stored serum for immunogenicity ^c			X			X	X	X	X

Notes. a) Elements of each panel are listed in Section 7.1.1

b) PK sample on Day 0 includes baseline (pre-infusion), 1 hour (+/- 15 min) after the end of the infusion, and 6 hours (+/- 30 min) after the end of the infusion.

c) Serum will be collected for immunogenicity assessment for subjects at the time of an AE suggestive of hypersensitivity reaction (including serum sickness) even if the AE does not coincide with a visit in which immunogenicity assessment is planned.

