7.2 Measures of Pharmacokinetics and Immunogenicity

As noted in the schedule and text above, 8 mL or 16 mL of blood will be obtained for evaluation of pharmacokinetics and immunogenicity. It is anticipated this will be in a serum separator tube (this tube may change without amending the protocol). Serum will be collected for immunogenicity assessment for subjects at the time of an AE suggestive of hypersensitivity reaction (including serum sickness) even if the AE does not coincide with a visit in which immunogenicity assessment is planned.

Pharmacokinetics evaluations will be performed by PPD. As SAB-176 cannot be differentiated from human IgG, the pharmacokinetics evaluations will use Hemagglutination Inhibition assays.

This protocol will evaluate immunogenicity in several assays:

1. anti-IgG antibodies using rheumatoid factor
2. Anti-Drug (anti-SAB-176) Antibody (performed at SAB Biotherapeutics)

7.3 12-Lead ECG

A 12-lead ECG will be obtained according to the Schedule of Assessments.

The ECGs will be measured using an ECG machine that calculates the heart rate and measures PR, QRS, QT, and QTcF.

Subjects will be required to lie quietly in a supine position for at least 5 minutes.

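### The seven-day look-back for influenza illness in exclusion 6 lets a recently infected, symptom-free subject be dosed while his or her own titre may still be rising, and the HAI-based PK cannot separate that rise from SAB-176

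*Protocol*

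**What the plan says.** Three look-back periods in Protocol section 4.4 bear on antibody that is present at dosing but does not come from the product:

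- Item 6, influenza illness: "Subjects who have been laboratory confirmed or clinically diagnosed with influenza within seven days prior to infusion (by subject history) will be deferred from infusion". The same item adds: "Any subject with signs and symptoms of an active respiratory infection on the day of infusion will be deferred until the infection is cleared". Clearance is judged by the investigator.
- Item 16: "Receipt of blood products within 2 months prior to study drug administration (i.e. Day 0".
- Item 17: "Receipt of any vaccination within 30 days prior to study drug administration (i.e. Day 0".

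Section 7.2 states how PK is measured: "As SAB-176 cannot be differentiated from human IgG, the pharmacokinetics evaluations will use Hemagglutination Inhibition assays". Section 1.1 describes the product as active against "strains of Type A influenza (H1N1/H3N2) and both lineages of Type B influenza (Yamagata/Victoria". HAI and MN are also secondary endpoints in their own right (section 11.9.2).

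Note b to the Schedule of Assessments (section 6.3.1) gives the Day 0 sampling: "PK sample on Day 0 includes baseline (pre-infusion), 1 hour (+/- 15 min) after the end of the infusion", with a further sample at 6 hours. PK serum is then drawn on Days 1, 2, 3, 7, 21, 42 and 90. There is one pre-dose PK sample. Under section 6.3.4.3, the pregnancy test is the only baseline laboratory result that must be available before infusion.

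**The concern.** An HAI titre after dosing is the product's contribution plus the subject's own anti-influenza antibody. If the subject's own part is constant, the pre-infusion value removes it. If it is rising, the pre-infusion value understates the later background, and the difference is counted as SAB-176.

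A recent influenza infection is a plausible source of such a rise. Item 6 is written as a rule about acute illness and does not address this. If the situation occurs, the PK profile and the neutralization results of the affected subject are overstated. With 2, 4, 6 and 8 SAB-176 recipients in the four cohorts, one subject carries real weight in the small ones. The cohorts are dosed one after another in a study planned to last one year, so exposure to circulating influenza could also differ between dose levels.

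**Working it through.** **Which subjects pass.** Item 6 covers days 0 to 7 before infusion and item 17 covers days 0 to 30. The stretch covered for vaccination but not for illness is days 8 to 30, that is 23 days. No other criterion reliably closes it. Item 7 concerns other intercurrent infections, items 11 and 18 rest on investigator judgement, and there is no titre criterion.

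**Inputs.** From Table 1: doses of 1, 10, 25 and 50 mg/kg, with 2, 4, 6 and 8 subjects on SAB-176 (20 in all; with 1 + 2 + 2 + 2 = 7 controls this gives the stated 27). Assumed, because the protocol gives no figures: titres add; true half-life 21 days; own pre-dose titre 40, rising to 80 (twofold) or 160 (fourfold) by Day 21; SAB-176 contribution at 1 hour of 320 in Cohort 1, proportional to dose thereafter.

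**Day 21 reading after subtracting the pre-dose value.** Reading = C0/2 + own Day 21 titre − 40. Two-point apparent half-life = 21 × ln 2 / ln(C0/reading). For the fourfold rise the excess is 160 − 40 = 120:

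| Cohort | C0 | True part, Day 21 | Reading | Excess | Apparent half-life (days) |
|---|---|---|---|---|---|
| 1 | 320 | 160 | 280 | 75% | 109 |
| 2 | 3,200 | 1,600 | 1,720 | 7.5% | 23.4 |
| 3 | 8,000 | 4,000 | 4,120 | 3% | 21.9 |
| 4 | 16,000 | 8,000 | 8,120 | 1.5% | 21.5 |

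For the twofold rise the excess is 40, which is 25%, 2.5%, 1% and 0.5%. The Cohort 1 half-life is then 21 × ln 2 / ln(320/200) = 31.0 days.

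**Later samples.** The two-point half-life is crude. Let the own titre rise linearly to Day 21 and then stay flat, and take the slope from Day 7 to Day 42. With f = 40/C0 and rise k, the signal is S(t) = 2^(−t/21) + f(k − 1) × min(t, 21)/21, and half-life = 35 × ln 2 / ln(S(7)/S(42)). For k = 4 this gives 63, 23.5, 22.0 and 21.5 days in Cohorts 1 to 4. For k = 1 it returns 21 days exactly, so the bias comes from the rise and not from the background level.

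**Effect on a cohort geometric mean from one affected subject.** Factor = (1 + excess)^(1/n). For the fourfold rise: 1.75^(1/2) = 1.32 in Cohort 1; 1.075^(1/4) = 1.02 in Cohort 2; below 1.01 in Cohorts 3 and 4.

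**Sensitivity to the anchor.** If 320 is instead the Cohort 4 value, Cohort 1 contributes 320/50 = 6.4 against an own titre of 40, so its PK is hard to read even without an infection. The fourfold rise then adds 120/160 = 75% in Cohort 4 and 120/80 = 150% in Cohort 3. The ordering by dose is the same under both anchors; the absolute size is not.

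**Chance of meeting such a subject.** With p the proportion of dosed subjects infected in the uncovered interval, P(at least one of 20) = 1 − (1 − p)^20. For p = 1%, 2%, 5% and 10% this is 18%, 33%, 64% and 88%. The protocol gives no value for p.

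**The case against.** The strongest reply is that the protocol does not contradict itself. Item 17 covers any vaccine and states no titre rationale, so the 30 days need not have been chosen to protect the assay, and item 6 is coherent as an acute-illness rule. This stands: the difference between the windows supports the point but does not prove an error. The argument rests on section 7.2.

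Second, nothing in the protocol says that a titre is still rising 8 to 30 days after diagnosis. This also stands; it is an assumption about antibody kinetics.

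Third, section 1.1 describes SAB-176 titres as extremely high, and doses span 50-fold. A reader might infer from the Cohort 1 row that a 75% excess and a half-life of 109 days apply throughout. They do not: one fixed drug titre cannot describe all four doses, and the half-life in that row uses two time points where the schedule provides many. Nor does one infection necessarily distort every strain, since Type A and Type B are assayed separately.

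Fourth, safeguards exist: the pre-infusion sample, saline controls in every cohort, medical history at screening, and an interval history at baseline that asks for new conditions. An SAP may specify baseline correction. These help only in part. One pre-dose value shows no slope, controls show the background of other subjects, and the history does not specifically require the date of the last influenza illness.

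A reader might also take item 6 to mean a seven-day deferral. It sets a look-back and gives no length of deferral; subjects with symptoms on the day wait until the infection is cleared.

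**Conclusion.** The point holds as a conditional weakness in eligibility. The protocol admits a symptom-free subject diagnosed with influenza 8 to 30 days before Day 0, and its PK assay cannot separate that subject's own rising titre from the product. If such a subject receives SAB-176, the HAI and MN readings and the apparent half-life for the matching strain would be too high.

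The relative effect is largest in Cohorts 1 and 2. It is probably small in Cohorts 3 and 4, provided that SAB-176 dominates the subject's own titre there, as the description in section 1.1 suggests. The size rests on assumed antibody kinetics and assumed titres. The frequency depends on overlap with an influenza season, which is unknown because the accrual dates are still to be determined.

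It would be tempting to conclude that the PK and neutralization results are biased as planned. The documents do not support that: without an affected subject on SAB-176 there is no bias from this source. Only secondary endpoints are involved; the primary safety endpoint is not. This is a cheap improvement, not a flaw that undermines the study.

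**What to change.** Reconcile items 6 and 17 of section 4.4 with the HAI-based PK in section 7.2. Add, with assay interference as the stated reason, an eligibility look-back for diagnosed influenza aligned with the vaccination window. Leave the acute-illness deferral in item 6 as it is. In sections 6.2.3 and 6.3.4.1, record the date of the last influenza illness, so that the PK and HAI/MN analyses can be repeated without any affected subject.

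The cost is about one line in section 4.4 and one recorded date. A few volunteers would be deferred or fail screening in season, against a ceiling of 150 screened to randomize 27. The change does not catch undiagnosed infection before dosing or any infection during the 90 days of follow-up.
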